11.5.5 Safety Precautions	

12.0 REFERENCES104

1.0 TRIAL SYNOPSIS

Title	A Phase Ib/II Trial of Interleukin-2 in Combination with Pembrolizumab for Patients with Unresectable or Metastatic Melanoma
Abbreviated Title	Pembrolizumab + IL-2
Trial Phase	Ib/II
Sites	[REDACTED]
Clinical Indication	Metastatic or unresectable melanoma
Trial Type	Interventional/Therapeutic
Type of control	None
Route of administration	IV
Trial Blinding	No
Trial Treatments	
 • Pembrolizumab 200mg IV Q3 weeks (flat dose) • IL-2 at 1 of 3 doses: 6,000, 60,000 or 600,000 IU/kg IV bolus Q 8H up to 14 doses at Weeks 4, 7, 16, 19, 28, and 31.
Treatment Groups	
 • Phase Ib Dose-escalation portion: Pembrolizumab 200mg IV Q3 weeks (flat dose) + IL-2 in escalating dose cohorts • Phase II: Pembrolizumab 200mg IV Q3 weeks (flat dose) + IL-2 at the maximum tolerated dose (MTD)
Study Design	
 • Pembrolizumab will be administered alone once as a loading dose, followed by concurrent administration of pembrolizumab and IL-2. • In the Phase Ib portion of the study, dose cohorts subjects will be treated with escalating doses of IL-2: 
 6,000 IU/kg, 60,000 IU/kg, or 600,000 IU/kg.

	
 • In the Phase II portion, patients will be treated with pembrolizumab and the MTD of IL-2. This will be a two-stage design for interim futility analysis based on response rate. • Patients who are benefitting from therapy may receive up to 3 courses (6 cycles) of IL-2. Patients will continue to receive pembrolizumab for up to 2 years.

Study Objectives
 
Primary
 
Secondary
	
 • To characterize the safety of IL-2 in combination with pembrolizumab. • To characterize the efficacy of IL-2 in combination with pembrolizumab. • To characterize the safety of IL-2 in doses ranging up to the FDA-approved dose when administered in combination with pembrolizumab. • To characterize clinical endpoints, including overall survival and progression-free survival, 1- and 2-year survival rates. • To characterize immune parameters in the blood and tumor microenvironment and cellular and molecular features of the tumor tissue

Study Endpoints
 
Primary
 
Secondary
	
 • Best objective response rate (BORR) according to RECIST v. 1.1, with the modification that progressive disease must be confirmed on a subsequent scan 4-6 weeks later. • Safety • Complete response rate • Progression-free survival • Overall survival at 1 and 2 years

Research Hypotheses
	
 • Combination therapy will result in a higher response rate than that which is previously reported for pembrolizumab monotherapy. • Combination therapy [REDACTED]

	
 • Combination therapy will lead to clinical endpoints that are better than those reported for pembrolizumab or IL-2 monotherapy. • Response to combination therapy will be associated with immune parameters in the blood and tumor microenvironment and cellular and molecular features of the tumor tissue.

Inclusion Criteria
	
 • Histologic or cytologic diagnosis of cutaneous melanoma, mucosal melanoma, or melanoma of unknown primary that is considered unresectable (Stage III) or metastatic (Stage IV). • Be willing and able to provide written informed consent/assent for the trial. • Be > 15 years of age on day of signing informed consent. • Have measurable disease evident on radiographs (preferred) or clinical examination. For this protocol, measurable disease is defined as at least one evaluable tumor that is at least 10 mm in longest dimension. • Have a performance status of 0 or 1 on the ECOG Performance Scale (See Appendix 11.1 for classification criteria). • Patients must have a brain MRI or CT (with and without contrast) that is free of active metastases. Metastases that have been treated with radiation or surgical resection, are stable for at least 4 weeks and do not require steroids are eligible. • Normal cardiac function. Patients who have a history of heart disease, or who are over the age of 50 years must have a normal cardiac stress test within the prior 90 days. • Normal lung function. Patients who have extensive pulmonary metastases or any chronic pulmonary disease history must have pulmonary function testing demonstrating FEV1 and FVC > 65% of predicted values. • Demonstrate adequate organ function (all screening labs should be performed within 10 days of treatment initiation): 
 ○ ANC ≥ 1,500/mcL ○ Platelets ≥ 100,000/mcL ○ Hemoglobin ≥ [REDACTED]

[REDACTED]


 ○ Creatinine $\leq 1.5 \times$ ULN or creatinine clearance ≥ 6 mL/min for subjects with creatinine levels $> 1.5 \times$ ULN ○ Serum total Bilirubin $\leq 1.5 \times$ ULN or Direct bilirubin \leq ULN for subjects with total bilirubin levels > 1.5 ULN. Patients with Gilbert's Syndrome must have a total bilirubin < 3.0 mg/dL. ○ AST/ALT $\leq 2.5 \times$ ULN or $\leq 5 \times$ ULN for patients with liver metastases ○ Albumin > 2.5 mg/dL ○ INR/PT $\leq 1.5 \times$ ULN unless subject is receiving anticoagulant therapy, as long as PT or PTT is within therapeutic range of intended use of anticoagulants ○ aPTT $\leq 1.5 \times$ ULN unless subject is receiving anticoagulant therapy, as long as PT or PTT is within therapeutic range of intended use of anticoagulants 
 ● Female subject of childbearing potential should have a negative urine or serum pregnancy test. If the urine test is positive or cannot be confirmed as negative, a serum pregnancy test will be required. ● Female subjects of childbearing potential must be willing to use 2 methods of birth control or be surgically sterile, or abstain from heterosexual activity for the course of the study through 120 days after the last dose of study medication. Subjects of childbearing potential are those who have not been surgically sterilized or have not been free from menses for > 1 year. ● Male subjects should agree to use an adequate method of contraception starting with the first dose of study therapy through 120 days after the last dose of study therapy. ● Subject meets institutional requirements for IL-2 therapy. 	

Exclusion Criteria
 
 ● Has primary ocular melanoma. ● Is currently participating and receiving study therapy or has participated in a study of an investigational agent and received study therapy or used an investigational device within 4 weeks of the first dose of treatment. ● Has a history of [REDACTED] matory bowel disease 	


• Has received systemic immunosuppressive steroid therapy or any other form of systemic immunosuppressive therapy for treatment of prior immune-related adverse events or other indications within 7 days prior to the first dose of trial treatment. Exception: Physiologic corticosteroid replacement therapy for adrenal or pituitary insufficiency is not considered systemic immunosuppressive steroid therapy.• Has received previous high dose ($\geq 600,000$ IU/kg) IL-2 therapy. Any other prior therapy (in the adjuvant or the metastatic setting) is allowed, including immunotherapy, targeted therapy, chemotherapy, and experimental therapy.• Has a history of significant congestive heart failure or significant pulmonary disease• Has a known history of active TB (Bacillus Tuberculosis)• Hypersensitivity to pembrolizumab or any of its excipients, or a known history of hypersensitivity to IL-2 or any component of the formulation.• Has had a prior anti-cancer monoclonal antibody (mAb) within 4 weeks prior to study Day 1 or who has not recovered (i.e., \leq Grade 1 or at baseline) from adverse events due to agents administered more than 4 weeks earlier.• Has had prior chemotherapy, targeted small molecule therapy, or radiation therapy within 2 weeks prior to study Day 1 or who has not recovered (i.e., \leq Grade 1 or at baseline) from adverse events due to a previously administered agent.
○ Note: Subjects with \leq Grade 2 neuropathy and/or alopecia are exceptions to this criterion and may qualify for the study.○ Note: If subject received major surgery, they must have recovered adequately from the toxicity and/or complications from the intervention prior to starting therapy.• Has a known additional malignancy that is progressing or requires active treatment. Exceptions include basal cell carcinoma of the skin or squamous cell carcinoma of the skin that has undergone potentially curative therapy or in situ cervical cancer.	
---	--

	
• Has known active central nervous system (CNS) metastases and/or carcinomatous meningitis. Subjects with previously treated brain metastases may participate provided they are stable (without evidence of progression by imaging for at least four weeks prior to the first dose of trial treatment and any neurologic symptoms have returned to baseline), have no evidence of new or enlarging brain metastases, and are not using steroids for at least 7 days prior to trial treatment. This exception does not include carcinomatous meningitis, which is excluded regardless of clinical stability.• Has a history of inflammatory bowel disease.• Has past medical history autoimmune disease (e.g. Crohn's disease, Rheumatoid arthritis, etc.) that has required systemic treatment in the past 2 years (i.e. with use of disease modifying agents, corticosteroids or immunosuppressive drugs).• Has a history of (non-infectious) pneumonitis that required steroids or current pneumonitis.• Has an active infection requiring systemic therapy.• Has a history or current evidence of any condition, therapy, or laboratory abnormality that might confound the results of the trial, interfere with the subject's participation for the full duration of the trial, or is not in the best interest of the subject to participate, in the opinion of the treating investigator.• Has known psychiatric or substance abuse disorders that would interfere with cooperation with the requirements of the trial.• Is pregnant or breastfeeding, or expecting to conceive or father children within the projected duration of the trial, starting with the pre-screening or screening visit through 120 days after the last dose of trial treatment.• Has a known history of Human Immunodeficiency Virus (HIV) (HIV 1/2 antibodies).• Has known active Hepatitis B (e.g., HBsAg reactive) or Hepatitis C (e.g., HCV RNA [qualitative] is detected).• Has received a live vaccine within 30 days of planned start of study therapy.
--	--

Criteria for Evaluation: (Efficacy, safety, stopping rules, etc.)
	
 Efficacy will be based on tumor assessments at specified time points. RECIST v1.1 will be used, with a modification to add a requirement that progressive disease must be confirmed on a subsequent scan 4-6 weeks later. Adverse events will be evaluated by NCI CTCAE, version 4.0.

Statistics:
	
Sample Size
 
 The total sample size is 60 evaluable subjects (approximately 12 for Phase Ib and 48 for Phase II). We anticipate enrolling 62-65 patients in order to obtain 60 evaluable patients. 
A phase Ib Dose-escalation portion will be conducted to determine the MTD, followed by a two-stage Phase II study.
 
Definition of Positive Primary Endpoint
 
 We will deem this approach meritorious of further study if toxicity is acceptable and 
 If the BORR is 30% or more, or If the complete response rate exceeds 20%, or If the 1 year overall survival rate exceeds 80%. 
Subgroup Analysis of Primary Endpoint:
 
 BORR will be analyzed by the following characteristics known or suspected to affect clinical outcomes: 
 PD-L1 positive vs. negative B-RAF mutated vs. wild type Prior treatment with checkpoint inhibitor vs. not ECOG 1 vs. 0 LDH elevated vs. normal Metastases limited to skin, lymph nodes, and lungs vs. other distant metastases 
Analysis of Secondary Objectives
 
 The frequency of AEs and SAEs will be recorded. In addition, data on the inpatient course will be summarized, including the duration of hospital [REDACTED]

	
interventions (transfer to a higher level of care, use of vasopressor, or use of supplemental oxygen) will be summarized.
 
 • Clinical measures of efficacy will be described, including overall survival, progression-free survival, need for additional therapy. • Descriptive statistical will be used, except where otherwise specified. Continuous variables will be presented by summary statistics (such as mean, median, standard error and 90% CI) and the categorical variables by frequency distributions (i.e., frequency counts, percentages and 90% CI). 
Analysis of Exploratory Objectives
 
 • Evaluation of immunological responses will be primarily based on the breadth and magnitude of cellular responses. The frequency of tumor specific T cells and regulatory cells including CD4+ Tregs and effector CD8+ will be measured pre-treatment and various days post-treatment in the tumor, when possible, and peripheral blood. Treatment effect for each patient will be measured as paired differences between pre and post measurements of these parameters at various times. Transformation of the data will be performed if appropriate, e.g. log transformation, and hence treatment effect will be expressed on a log scale.

Correlative Studies
	
Tumor Microenvironment
 
 • PD-L1 staining • Frequency of effector CD8+ T cells • Frequency of CD4+FoxP3+ regulatory T cells 
Peripheral Blood
 
 • Analysis of lymphocyte and myeloid cell subpopulations using flow cytometry • Chemokine/cytokine measurements • Serum VEGF, fibronectin, and CRP levels • Melanoma antigen specific T cell responses and antibodies

Number of trial subjects
	
60-65

Estimated enrollment period	24 months
Estimated duration of trial	36 months
Duration of Participation	Up to 2 years

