5.1.2 Subject Inclusion Criteria

In order to be eligible for participation in this trial, the subject must:

1. Histologic or cytologic diagnosis of cutaneous melanoma, mucosal melanoma, or melanoma of unknown primary that is considered unresectable (Stage III) or metastatic (Stage IV).
2. Be willing and able to provide written informed consent/assent for the trial.
3. Be ≥ 15 years of age on day of signing informed consent.
4. Have measurable disease evident on radiographs (preferred) or clinical examination. For this protocol, measurable disease is defined as at least one evaluable tumor that is at least 10 mm in longest dimension.
5. Have a performance status of 0 or 1 on the ECOG Performance Scale (See Appendix 11.1 for classification criteria).
6. Patients must have a brain MRI or CT (with and without contrast) that is free of active metastases. Metastases that have been treated with radiation or surgical resection, are stable for at least 4 weeks and do not require steroids are eligible.
7. Normal cardiac function. Patients who have a history of heart disease, or who are over the age of 50 years must have a normal cardiac stress test within the prior 90 days.

8. Normal lung function. Patients who have extensive pulmonary metastases or any chronic pulmonary disease history must have pulmonary function testing demonstrating FEV1 and FVC > 65% of predicted values.
9. Demonstrate adequate organ function as defined in Table 1,

Table 1. Adequate Organ Function Laboratory Values

System	Laboratory Value
Hematological	
Absolute neutrophil count (ANC)	≥1,500 /mcl
Platelets	≥100,000 / mcl
Hemoglobin	≥9 g/dL or ≥5.6 mmol/L without transfusion or EPO dependency (within 7 days of assessment)
Renal	
Serum creatinine OR Measured or calculated* creatinine clearance (GFR can also be used in place of creatinine or CrCl)	≤1.5 X upper limit of normal (ULN) OR ≥60 mL/min for subject with creatinine levels > 1.5 X institutional ULN
Hepatic	
Serum total bilirubin	≤ 1.5 X ULN OR Direct bilirubin ≤ ULN for subjects with total bilirubin levels > 1.5 ULN. Patients with Gilbert's Syndrome must have a total bilirubin < 3.0 mg/dL.
AST (SGOT) and ALT (SGPT)	≤ 2.5 X ULN OR ≤ 5 X ULN for subjects with liver metastases
Albumin	>2.5 mg/dL
Coagulation	
International Normalized Ratio (INR) or Prothrombin Time (PT)	≤1.5 X ULN unless subject is receiving anticoagulant therapy as long as PT or PTT is within therapeutic range of intended use of anticoagulants

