Activated Partial Thromboplastin Time (aPTT)	≤1.5 X ULN unless subject is receiving anticoagulant therapy as long as PT or PTT is within therapeutic range of intended use of anticoagulants

*Creatinine clearance should be calculated per institutional standard.

10. Female subject of childbearing potential should have a negative urine or serum pregnancy test. If the urine test is positive or cannot be confirmed as negative, a serum pregnancy test will be required.

11. Female subjects of childbearing potential must be willing to use 2 methods of birth control or be surgically sterile, or abstain from heterosexual activity for the course of the study through 120 days after the last dose of study medication. Subjects of childbearing potential are those who have not been surgically sterilized or have not been free from menses for > 1 year.
12. Male subjects should agree to use an adequate method of contraception starting with the first dose of study therapy through 120 days after the last dose of study therapy.
13. Subject meets institutional requirements for IL-2 therapy.

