5.7.2 Contraception

Pembrolizumab and IL-2 may have adverse effects on a fetus in utero. Furthermore, it is not known if pembrolizumab has transient adverse effects on the composition of sperm. Non-pregnant, non-breast-feeding women may be enrolled if they are willing to use 2 methods of birth control or are considered highly unlikely to conceive. Highly unlikely to conceive is defined as 1) surgically sterilized, or 2) postmenopausal (a woman who is ≥ 45 years of age and has not had menses for greater than 1 year will be considered postmenopausal), or 3) not heterosexually active for the duration of the study. The two birth control methods can be either two barrier methods or a barrier method plus a hormonal method to prevent pregnancy. Subjects should start using birth control from study Visit 1 throughout the study period up to 120 days after the last dose of study therapy.

The following are considered adequate barrier methods of contraception: diaphragm, condom (by the partner), copper intrauterine device, sponge, or spermicide. Appropriate hormonal contraceptives will include any registered and marketed contraceptive agent that contains an estrogen and/or a progestational agent (including oral, subcutaneous, intrauterine, or intramuscular agents).

Subjects should be informed that taking the study medication may involve unknown risks to the fetus (unborn baby) if pregnancy were to occur during the study. In order to participate in the study they must adhere to the contraception requirement (described above) for the duration of the study and during the follow-up period defined in section 7.2.5-Reporting of Pregnancy

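### Criterion 11 and the synopsis define childbearing potential without the age-45 condition of Section 5.7.2; separately, the synopsis clearance limit of 6 mL/min (60 in Table 1) should be corrected if the source page confirms it

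*SAP*

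**What the plan says.** **Childbearing potential.** The synopsis inclusion list (SAP, Section 1.0) states: "Subjects of childbearing potential are those who have not been surgically sterilized or have not been free from menses for > 1 year". Criterion 11 in Section 5.1.2 repeats the sentence word for word, ending "have not been free from menses for > 1 year". Neither place mentions age. The main clause of criterion 11 asks women of childbearing potential to use two methods of birth control, to be surgically sterile, or to abstain. Criterion 10 ties testing to the same label: "Female subject of childbearing potential should have a negative urine or serum pregnancy test".

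Section 5.7.2 (Contraception) is worded as a condition of enrolment. Women who are neither pregnant nor breast-feeding may enter if they will use two methods or are highly unlikely to conceive. The latter means surgically sterilized, postmenopausal, or not heterosexually active. For the second of these, a woman of at least "45 years of age and has not had menses for greater than 1 year will be considered postmenopausal". The section also says that the two drugs "may have adverse effects on a fetus in utero".

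**Renal function.** For subjects with creatinine above 1.5 x ULN, the supplied synopsis text sets a creatinine-clearance limit of at least "6 mL/min for subjects with creatinine levels" above that threshold. The corresponding row of Table 1 (Section 5.1.2) reads "60 mL/min for subject with creatinine levels". Criterion 9 makes Table 1 the operative standard: "Demonstrate adequate organ function as defined in Table 1".

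**The concern.** Two places that both bear on entry sort some women differently. The natural reading of criterion 11 is that a woman who has been sterilized, or who has gone more than a year without menses, is not of childbearing potential. A woman under 45 with amenorrhea then falls outside criterion 10, so the numbered criteria do not call for a pregnancy test. Section 5.7.2 does not regard the same woman as postmenopausal. Criterion 3 admits subjects from age 15, so women under 45 are within scope. What is at stake is consistent testing and contraception for drugs that the protocol itself says may harm a fetus.

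The renal limit raises a simpler question. A site that screens from the synopsis list, which carries its own figures, could see a limit ten times lower than the one in Table 1.

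**Working it through.** No figure in the plan needs reproducing; this is a comparison of texts.

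**Step 1: the three rules.** Let S = surgically sterilized and A = more than 1 year without menses. Abstinence is left aside because both places accept it.

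- Section 5.7.2, highly unlikely to conceive: S or (A and age at least 45).
- Criterion 11, ordinary reading, not of childbearing potential: S or A.
- Criterion 11, literal reading. Childbearing potential is (not S) or (not A), so a woman lacks it only if S and A.

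**Step 2: all 2 x 2 x 2 = 8 combinations** (yes = exempt).

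| Row | S | A | Age | Section 5.7.2 | Criterion 11, ordinary | Criterion 11, literal |
|---|---|---|---|---|---|---|
| 1 | yes | yes | under 45 | yes | yes | yes |
| 2 | yes | yes | 45 or more | yes | yes | yes |
| 3 | yes | no | under 45 | yes | yes | no |
| 4 | yes | no | 45 or more | yes | yes | no |
| 5 | no | yes | under 45 | no | yes | no |
| 6 | no | yes | 45 or more | yes | yes | no |
| 7 | no | no | under 45 | no | no | no |
| 8 | no | no | 45 or more | no | no | no |

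The ordinary reading differs from Section 5.7.2 in 1 of 8 (row 5), where criterion 11 is looser. The literal reading differs on the label in 3 of 8 (rows 3, 4 and 6), where criterion 11 is stricter.

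**Step 3: what each difference means in practice.**

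- *Ordinary reading, row 5.* Criteria 10 and 11 ask for neither test nor contraception. Section 5.7.2 separately requires two methods. Entry conditions are cumulative, so contraception is required and only the test is unaddressed.
- *Literal reading, rows 3 and 4.* Criterion 11 accepts surgical sterility in place of birth control. The contraception rules therefore agree, and only the label and the criterion 10 test differ.
- *Literal reading, row 6.* Criterion 11 asks for contraception and Section 5.7.2 does not. This is the only contraception difference, 1 of 8.
- *Literal reading, row 5.* The woman is of childbearing potential, so test and contraception both apply.

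**Step 4: renal limit.** 60 / 6 = 10. A subject with creatinine above 1.5 x ULN and clearance from 6 to below 60 mL/min meets the synopsis as supplied and fails Table 1. Table 1 has 9 rows. The synopsis haemoglobin value is redacted, leaving 8 to compare: ANC, platelets, creatinine or clearance, bilirubin, AST/ALT, albumin, INR/PT and aPTT. The limits agree in 7 and differ only here, which points to a dropped zero and not to a second standard.

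**The case against.** The best defence is that the printed *or*, taken as written, already makes the younger woman with amenorrhea a subject of childbearing potential, so criteria 10 and 11 both reach her. That is correct on the literal reading. It does not remove the inconsistency, because the definitions then part for the older woman in row 6, and for sterilized women on the label and the test.

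A reader might infer that such a younger woman could enter with neither a pregnancy test nor contraception. The documents do not support that. Section 5.7.2 binds her to contraception and limits enrolment to women who are not pregnant, and exclusion 18 bars pregnant subjects. What stands is narrower: on the ordinary reading, no supplied text mandates a test for her. Even this may be closed elsewhere, since the flow chart (Section 6.0) and laboratory procedures (Section 7.1.5) are not in the supplied text.

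A reader might also take 3 of 8 as the size of the contraception conflict on the literal reading. It is 1 of 8. Section 5.7.2 as supplied defines who is unlikely to conceive and does not itself set a pregnancy-test rule, so the other two cells concern only the label and criterion 10.

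On clearance, the objection is that Table 1 is operative through criterion 9 and that a digit may have been lost when text was extracted from the PDF. Both stand, so the point is conditional. A reader might go further and suppose that patients were admitted below 60 mL/min, or that enrolled patients need a retrospective check. Nothing in the documents indicates that the synopsis was used to enrol anyone.

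**Conclusion.** The main point holds as a minor inconsistency. Two statements that bear on entry define the same group of women differently, and they do so on either reading of criterion 11. On the ordinary reading the practical residue is one missing pregnancy-test requirement, for unsterilized women under 45 with more than 1 year of amenorrhea. On the literal reading it is extra contraception for unsterilized women of 45 or more with more than 1 year without menses, plus differences of label and test. This assumes that Section 5.7.2 applies at entry alongside the numbered criteria, as its wording indicates, and that the sections not supplied add no testing rule. The number of women affected cannot be derived from the documents.

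The clearance point is secondary: a tenfold difference in a printed limit if the source page reads 6, and nothing if it reads 60. Neither point touches sample size, power or analysis.

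**What to change.** In criterion 11 and in the synopsis, replace the childbearing sentence with the Section 5.7.2 definition: a woman is not of childbearing potential if she is surgically sterilized, or if she is aged 45 or more and has gone more than 1 year without menses. Younger women with amenorrhea then come under both testing and contraception. Against the literal reading this also lifts the criterion 10 test in rows 3, 4 and 6 and the contraception requirement in row 6, so the sponsor should confirm that this is intended.

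Check the synopsis source page for the clearance limit. If it reads 6, change it to 60 mL/min or refer the reader to Table 1. No check of enrolled patients is warranted on the documents.

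The cost is one sentence in each of two places and, if confirmed, one figure in the synopsis. There is no analysis cost.

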use of high-dose bolus IL-2 for the treatment of metastatic melanoma in 1998. Further follow-up on these pivotal studies suggested that patients can achieve durable long-term benefit from IL-2. After a median follow-up time for surviving patients that exceeded 7 years, the median duration of response for 43 responding patients and the 26 patients with partial responses in the pivotal IL-2 trials remained unchanged at 8.9 and 5.9 months, respectively [17]. Response durations ranged from 1.5 to > 122 months and disease progression had not been observed in any patient who was responding as of the last report or in any patient responding for longer than 30 months [17].

In these early trials, the most severe toxicities were related to a vascular leak syndrome that resembled the manifestations of septic shock. Sixty-four percent of patients experienced hypotension, while 1% suffered grade 4 hypotension. Other severe toxicities included mental status changes, tachyarrhythmia, and respiratory events, but these were rare, occurring in less than 4% of patients. Nausea, vomiting, and diarrhea were common, but were not life-threatening. Elevations of serum creatinine and bilirubin were frequent but did not lead to chronic organ dysfunction. Infections were seen in 15% of all patients, with bacterial sepsis due to *Staphylococcus aureus* leading to 6 treatment-related deaths. In 1990, antibiotic prophylaxis became standard practice during IL-2 therapy and treatment-related mortality decreased significantly [33]. There are now well established treatment guidelines for the prevention and management of high-dose IL-2-related toxicity [34]. Since the approvals of the immune checkpoint inhibitors, IL-2 is mostly being used as a salvage regimen and is not frequently used as a first-line therapy.

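### The albumin entry limit is written as more than 2.5 mg/dL in both copies of the organ-function criteria, so as written it excludes nobody; the unit appears to be wrong.

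*SAP*

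**What the plan says.** The albumin limit appears twice in the SAP document. The inclusion criteria in the trial synopsis (Section 1.0) list "Albumin > 2.5 mg/dL" among the organ-function values. Table 1 in Section 5.1.2 repeats the limit in its hepatic block with the same number and unit. Table 1 is binding, because inclusion criterion 9 requires the subject to "Demonstrate adequate organ function as defined in Table 1". No other albumin limit was found in the text reviewed.

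Two neighbouring entries show how units are used elsewhere in the same criteria:

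- Hemoglobin in Table 1 is "≥9 g/dL or ≥5.6 mmol/L without transfusion or EPO dependency (within 7 days of assessment", that is, in g/dL with a molar equivalent.
- Bilirubin, in the same hepatic block as albumin, has a limit in mg/dL: "Patients with Gilbert's Syndrome must have a total bilirubin < 3.0 mg/dL".

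**The concern.** An entry limit does its work only if some patients could fail it. Serum albumin is ordinarily measured in grams per decilitre, so a limit of 2.5 milligrams per decilitre lies far below any value a patient is likely to have. The two copies agree, so comparing the synopsis with the body of the protocol would not expose the problem.

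What is at stake is one numeric line in a set of binding, safety-related entry criteria. If the line is inert, the protocol's stated albumin requirement does not operate. If staff silently read it in another unit, the rule being applied is one that the protocol does not state. Nothing in the text would then settle whether admitting a patient at, say, 2.0 g/dL was a deviation.

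**Working it through.** **Inputs**

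- Written limit: more than 2.5 mg/dL (synopsis and Section 5.1.2, Table 1).
- Unit conversion: 1 g = 1000 mg.
- Serum albumin range: the documents give none. The assumption here is 1.0 to 5.5 g/dL, with 0.2 g/dL added as an extreme low value.

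**Step 1. Convert the limit.** 2.5 mg/dL ÷ 1000 = 0.0025 g/dL.

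**Step 2. Compare it with the assumed values.** Ratio = (albumin in g/dL × 1000) ÷ 2.5.

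| Assumed albumin (g/dL) | In mg/dL | Multiple of written limit | Passes as written? |
|---|---|---|---|
| 0.2 (extreme) | 200 | 80 | yes |
| 1.0 | 1000 | 400 | yes |
| 1.5 | 1500 | 600 | yes |
| 2.0 | 2000 | 800 | yes |
| 2.5 | 2500 | 1000 | yes |
| 3.5 | 3500 | 1400 | yes |
| 5.0 | 5000 | 2000 | yes |
| 5.5 | 5500 | 2200 | yes |

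Every value passes, including the extreme one.

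**Step 3. See whether the same number discriminates in another unit.** This is for scale only.

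- In g/dL, the limit would be 2500 mg/dL. Assumed values of 1.0, 1.5, 2.0 and 2.5 g/dL would fail, and 3.5 to 5.5 g/dL would pass.
- In g/L, it would be 2.5 ÷ 10 = 0.25 g/dL. That is below the whole assumed range, so again nobody in the range would fail.

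Of the three units, only g/dL makes the number separate patients within the assumed range. This points to a unit error but does not establish what the sponsor intended.

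**Step 4. Check the neighbouring units.** With the usual conversion factor, hemoglobin of 9 g/dL × 0.6206 = 5.6 mmol/L, which agrees with Table 1. Units in that row were therefore handled correctly. The bilirubin row, two rows above albumin, uses mg/dL. Carry-over from that row would explain the albumin entry, but that is inference.

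**The case against.** The strongest reply is that this is a slip any experienced site will read through. Step 3 supports it: only one of the three units gives a working limit, so the likely practical effect is a query rather than different populations. That limits the harm but leaves the text wrong, because the rule then applied is still not the one written.

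Four stronger readings are tempting, and the documents do not support them.

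- **The limit is 1000-fold below any measurable value.** A factor of 1000 is simply the ratio of mg to g, and it is the gap only at 2.5 g/dL. Over the assumed range the gap is 400 to 2200 times.
- **There is no safety screen, and a patient with very low albumin is eligible.** Only this line is inert. Inclusion criterion 13 requires that institutional requirements for IL-2 be met. Exclusion criterion 16 lets the investigator exclude a patient because of a laboratory abnormality. The cardiac, lung, performance-status, renal, hepatic and coagulation criteria also still apply. These are discretionary or indirect and state no albumin limit, but they can stop such a patient.
- **Sites will admit different patients, or an electronic check will pass everyone.** No eligibility checklist or case report form was available. Sections 7.1.5 (laboratory procedures) and 10.8.2 (case report forms) were available only as contents entries. These outcomes are possible but not shown.
- **The protocol relies on albumin to guard against vascular leak.** Section 4.1.3.2 says of the early IL-2 trials that "the most severe toxicities were related to a vascular leak syndrome that resembled the manifestations of septic shock", but it does not mention albumin. The link is the reader's, not the protocol's.

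A fault in reading the PDF is also unlikely, because two separately formatted entries carry the same unit.

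**Conclusion.** The point holds for this one criterion. As written, the albumin limit is 0.0025 g/dL and excludes nobody in the assumed range of 1.0 to 5.5 g/dL. The conclusion is not sensitive to that assumption, since even 0.2 g/dL is 80 times the limit. The unit appears to be wrong, judging by the units used for hemoglobin and bilirubin in the same table. The documents do not say which unit and number were intended.

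The consequence is confined to eligibility: the protocol's own numeric albumin requirement has no effect, and only the discretionary or indirect criteria remain for very low albumin. No sample size, error rate, power or endpoint depends on it. It merits correction because it sits in a binding entry criterion rather than in background text.

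**What to change.** The sponsor should confirm both the intended unit and the intended number for the albumin limit, then correct the synopsis and Table 1 in Section 5.1.2 in the same amendment so that the copies stay aligned. Any eligibility checklist, laboratory section or data-entry check built from these criteria should be compared with the confirmed limit and changed if it differs.

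The cost is a text correction in two places, plus the check of derived documents and whatever updates that shows to be needed. The design and the analysis do not change.

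If patients have already been enrolled, a listing of their baseline albumin against the confirmed limit would show whether the wording affected anyone.
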